Aims 2 and 3: To compare self-care continuous outcomes and clinical continuous outcomes including A1C (primary outcome) over the three study groups, a repeated measure analysis of variance via LMM will be performed to model one outcome over time and test the effects of treatment, time and their interaction. Clinic will be considered as random effects in a LMM to account for within-site association. We will fit an unadjusted model first and then an adjusted model adjusting for baseline outcome and participant-level potential confounders as mentioned above. Normality will be checked and appropriate data transformation will be performed if data highly skewed. The p-value for the group comparison between MDG and MDG+CRx in A1C at 12 months will be used for the primary objective analysis at the two-sided significance level of 5% (consistent to the power justification (below)). Multiple pairwise comparisons will be conducted to compare between groups at each time point and compare the multiple time points within a group. All the multiple comparisons and analyses of all the secondary outcomes will be considered to be exploratory and will not spend the overall type I error rate of 5%. To compare each of binary outcomes such as utilization of community-based resources, we will use GEE and GLMM for group comparisons, as mentioned in analyses of Aim 1. To compare health care use (ED and hospitalizations), we will use both Poisson and negative binomial regression models. If the health care use data are zero-inflated (i.e., >50% of patients who have no service use), we will use both zero-inflated Poisson and zero-inflated negative binomial models.

Sensitivity analyses: We will also assess the impact of our interventions across patient subgroups (age group, health status, baseline A1C group, and diabetes duration with different thresholds).

Interim analyses: We will apply the statistical methods above to all the available data including baseline, all 6-month follow-up data, and about 75% 12-month follow-up data.

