Qualitative interview data will be systematically collected and analyzed using rapid qualitative methods.¹¹⁷ Rapid qualitative methods are well-suited for mixed methods studies and commonly used in implementation science studies when quick understanding of qualitative data is needed to inform next steps or to help interpret or triangulate findings. Rapid qualitative methods use constant comparison of data to inform continued data collection, and analysis is conducted during data collection through the use of text summaries.

Focus groups will be audio-recorded to ensure the accuracy of participants' responses. Researchers will create a data analysis template that includes a neutral domain name that corresponds with each focus group question. Trained researchers will listen to the audio of each focus group session and create a summary of each domain, with space for other observations that may occur during data collection. Then, all text summaries will be collated into one matrix (focus group x domain) and assessed for similarities and differences across responses and by

domain. Matrices may also be set up by individual focus group or by respondent study arm (e.g., pooling all responses for those who participated in the intervention group), if appropriate. Matrices will be analyzed for gaps in the data, emergent themes and to generate summaries of responses from participants in each study arm.

Addition of a Usual Care Arm

To assess whether the experience of the participants within the trial differs from patients at UCM who did not participate in the trial during the study timeframe, we will include a Usual Care Arm based on the original eligibility criteria used to generate the ACRES recruitment lists of patients and include retrospective outcomes data (A1C and medications between 9-23-2020 to 9-16-2024).

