Among the 167 patients who were enrolled in attention control arm, 133 patients had an A1C result in EHR at 12 month follow up by May of 2024. These patients had an average reduction of 0.97% (SD 1.64%) in A1C from baseline to 12 month. Based on our literature review, we found no consistent pattern for A1C change in usual care arms in behavioral intervention trials published in 2023 and 2024.¹¹⁸⁻¹²⁹ Based on this finding, we assume no A1C change will be observed in our usual care arm. By a two-sample t-test, a sample size of 39 in the usual care arm would guarantee $\geq 90\%$ power to detect at least 0.97% difference in A1C with the common SD of 1.64% between the attention control arm and usual care arm with a two-sided significant level of 5%. To account for up to 20% of subject attrition at 12 months, the final total sample size of the usual care arm is 49.

For simplicity, we plan to conduct a 1:1 matching for the usual care arm vs attention control arm (i.e., 167 patients will be included in the usual care arm). The matching procedure involves three steps. First, we identify all the potential usual care arm patients using the original eligibility criteria and have CRI generate a deidentified (except month and year of dates) list of patients at UCM excluding those who were enrolled in the study and ages over 89. Second, we will only include patients who have an A1C $\geq 7.5\%$ within our trial recruitment time (09-23-2021 to 07-07-2023). Third, we use R MatchIt package to perform the matching. We use exact matching on A1C group (7.5-8, 8-8.5, 8.5-9.5, 9.5+) and the calendar quarter using month and year when the A1C test was conducted. This step ensures patients who are enrolled in the usual care arm have similar A1C values and baseline dates as the attention control arm. We will also use propensity score matching on other covariates, such as age, gender, race/ethnicity. After the matching, we test the balance of the data on these covariates.

J. Potential risks and benefits

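### Usual care versus attention control: band matching leaves baseline A1C uncontrolled above 9.5, and no outcome model with continuous baseline A1C is stated (minor)

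*Combined protocol and SAP*

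**What the plan says.** All of this is in Section I, Statistical analysis.

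- **Matching** (Addition of a Usual Care Arm): "We use exact matching on A1C group (7.5-8, 8-8.5, 8.5-9.5, 9.5+) and the calendar quarter". The plan then states: "This step ensures patients who are enrolled in the usual care arm have similar A1C values".
- **Propensity score** (same subsection): "We will also use propensity score matching on other covariates, such as age, gender, race/ethnicity". The list is open, but A1C is not among the examples, and the word other most naturally sets A1C aside as already handled.
- **Balance check** (same subsection): "After the matching, we test the balance of the data on these covariates".
- **Test named** (same subsection): "By a two-sample t-test, a sample size of 39 in the usual care arm would guarantee" at least 90% power. The inputs are the attention-control arm's mean A1C reduction of 0.97 (SD 1.64) and an assumed change of zero under usual care. No outcome model is given for the comparison itself.
- **Baseline adjustment elsewhere** (Aims 2 and 3): "We will fit an unadjusted model first and then an adjusted model adjusting for baseline outcome and participant-level potential confounders". That model is introduced for A1C and the other continuous outcomes "over the three study groups, a repeated measure analysis of variance via LMM will be performed". The usual-care text comes later and does not refer back to it.

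**The concern.** In the three closed bands, two matched patients differ by at most 0.5 or 1.0 point. In the band from 9.5 upward, a patient at 9.6 and one at 14 count as an exact match. The claim of similar A1C values therefore fails in the band where values can differ most.

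The planned balance check need not reveal this. Even if its covariates include the A1C group, exact matching balances the group by construction, so the check cannot show a difference inside 9.5+.

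The arms are not randomized: one was recruited and consented, and the other is drawn from records of patients who were not enrolled. Patients who start higher tend to fall further. If one arm has a heavier tail above 9.5, part of that baseline gap passes into the difference in A1C change and would be read as an effect of attention or of trial participation.

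**Working it through.** **1. The plan's own figure.** Inputs: difference 0.97, SD 1.64, two-sided 5%, 133 attention-control patients with a 12-month A1C, 39 usual-care patients.

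- SE = 1.64 × √(1/39 + 1/133) = 0.299.
- 0.97/0.299 = 3.25, and Φ(3.25 − 1.96) = 0.90.
- 39/0.8 = 48.75, rounded up to 49.

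The figures reproduce. With about 133 and 134 analysed, power for 0.97 is 99.8%, so sample size is not the issue.

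**2. What band matching leaves.** Residual baseline gap = Σ over bands of (attention-control share) × (attention-control mean − usual-care mean). Bias in the difference in change = slope × gap, where slope is the fall in A1C per point of baseline.

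Assumptions, since the documents give neither distribution nor slope: A1C above 7.5 is exponential with mean excess 1.6 in attention control, and slope is 0.5. The share at 9.5+ is exp(−2/1.6) = 0.287. Within that band, the gap is 1.6 × (1 − ratio of the mean excesses).

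| Usual-care excess | Gap in 9.5+ | × 0.287 | Closed bands add | Total gap | Bias (× 0.5) |
|---|---|---|---|---|---|
| equal | 0 | 0 | 0 | 0 | 0 |
| 10% lower | 0.16 | 0.046 | 0.002 | 0.048 | 0.024 |
| 20% lower | 0.32 | 0.092 | 0.005 | 0.096 | 0.048 |
| 30% lower | 0.48 | 0.138 | 0.008 | 0.145 | 0.073 |

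Almost all of the gap comes from the open band. A usual-care excess 10 to 30% higher gives nearly the same sizes with the opposite sign.

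**3. Against the standard error.** 1.64 × √(2/167) = 0.179 and 1.64 × √(2/133) = 0.201. The biases are about 0.1, 0.2 to 0.3, and 0.4 of a standard error.

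**4. Wider assumptions.** The grid uses gamma shape 1 or 1.5, mean excess 1.3, 1.6 or 2.0, usual-care excess 10, 20 or 30% lower or higher, and slope 0.3 to 0.7 in steps of 0.1. That gives 180 equally weighted cells with median bias 0.041 and maximum 0.159. Adding equal tails (210 cells) gives minimum 0 and median 0.035. The equal weighting is arbitrary. If the t-test's standard error is taken at face value, a shift of 0.041 moves the two-sided type I error from 5% to about 5.5%.

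**5. Precision.** With slope 0.5 and baseline SD 1.6, the residual SD is √(1.64² − 0.5² × 1.6²) = √2.05 = 1.43. The standard error becomes 1.43 × √(2/133) = 0.176, against 0.201: about 12% smaller.

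That is the standard error the analysis would report. Matching has already removed part of the baseline variation, and an ordinary t-test does not credit it. I simulated 3,000 trials with no true effect: the step 2 assumptions, 167 attention-control patients, 1,670 donors, four bands by nine quarters, and 20% attrition.

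- With equal tails, the t-test reported a standard error of 0.200 while its estimates had an SD of 0.186. Regression gave 0.175 for both. The real gain in precision is therefore about 6%; the rest is a more accurate standard error.
- For the same reason the t-test rejected only 3.4% of the time with equal tails, and 5.4% with usual-care excess 30% lower. The 5.5% in step 4 is thus, if anything, on the high side.
- With usual-care excess 30% lower, the mean estimate was −0.070 by t-test and 0.003 by regression.

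**6. Balance inside 9.5+.** 0.287 × 167 ≈ 48 patients per arm. The sampling error of a standardized mean difference is about √(2/48) = 0.20, so values beyond 0.2 arise about a third of the time when the tails are equal.

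**The case against.** **The comparison is built on change, which already uses each patient's own continuous baseline.** True, and it narrows the point: baseline A1C is not ignored. But subtracting baseline is not adjusting for it. If change has slope 0.5 on baseline, half of any baseline gap remains in the difference in change.

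**The baseline-adjusted model for Aims 2 and 3 may be meant to apply, and the t-test is named only to justify the sample size.** This stands in part. A reader might infer that the plan commits to an unadjusted t-test. The documents do not say that; they name no analysis for this comparison. Equally, they do not extend the adjusted model to it. If that is the intention, saying so would largely settle the matter.

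**Nothing shows that the tails differ.** This stands. Both arms come from the same health system, under the original eligibility criteria, the same A1C floor and matching by calendar quarter. A reader might infer that the comparison is biased, or biased in favour of attention control. The documents support neither the existence nor the direction of a bias.

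**The effect is too small to change a conclusion.** Largely right for a difference near 0.97. It is less clear for a small observed difference, where a shift of 0.05 to 0.07 is a larger share of the result. The case for change rests on the remedy being nearly free, not on a demonstrated error.

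**Conclusion.** The point holds as a minor one. The statement that matching secures similar A1C values is not true inside 9.5+, and no stated analysis makes up for it. Under the assumed distributions the bias is zero with equal tails, about 0.02 to 0.05 points for a 10 to 20% difference in mean excess, and about 0.07 at 30%, which is the edge of the assumed range rather than a central value. All of these lie below half a standard error.

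The more certain benefit is a reported standard error of about 0.18 in place of 0.20, of which roughly half is a real gain in precision.

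Two stronger readings should be resisted. The gap cannot account for a difference of 0.97: the largest bias in the grid is 0.159. It also has no bearing on the primary test, which compares the two randomized intervention arms (MDG and MDG+CRx) on 12-month A1C.

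**What to change.** Keep the band and quarter matching and 167 per arm. Add one sentence: the comparison will be analysed by regressing 12-month A1C on group, continuous baseline A1C and the matching covariates, with a curved baseline term to check linearity, mainly above 9.5. This applies the baseline-adjustment principle of Aims 2 and 3 but is not the same model, which is a repeated-measures mixed model with clinic as a random effect.

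Report the standardized mean difference for continuous A1C overall. Give the figure within 9.5+ as description only, since it is noisy at about 48 patients per arm (under the assumed distribution) and should trigger no action. Reword the statement that the step secures similar A1C values so that it is limited to the closed bands.

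The cost is a sentence and a few lines of code. The planned extract ("A1C and medications between 9-23-2020 to 9-16-2024") already holds the data, and no patient is lost. The added assumption is a roughly linear baseline effect, which the curved term tests.
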